Clinical and Behavioral Testing: Risks in regard to the behavioral assessment are limited to fatigue, frustration and momentary embarrassment that may occur when one experiences difficulty disclosing information or during task performance. The overnight "off" state may result in discomfort and transient worsening of parkinsonism symptoms.

Adequacy of Protection Against Risks:

Recruitment and Informed Consent:

Subjects will be recruited from the UM Movement Disorders clinic and by advertisement. Individuals willing to participate will be scheduled for the research procedures at which time the nature and risks of the procedures will again be reviewed with the subjects and a written informed consent form will be obtained by one of the study investigators. One copy of the signed consent form will be given to the subject, one will be placed in the patient's medical record and a third will be kept in the patient's study binder kept at the patient's research site. Study visits will be conducted in [name] laboratory in East Hall at the University of Michigan.

Protection Against Risk:

Confidentiality of Research Information: The possibility of unintended disclosure of medical or research data is minimal, but not entirely impossible. We will employ stringent safeguards against unintended and inappropriate discovery and dissemination of personal medical and research data in our subjects by a multi-layered approach. All data bearing potential subject identifiers will reside solely in locked files in the offices of the study investigators. Original data collection documents will be maintained in secure files under the control of the investigators. Entries regarding details of the research project and its results will not be submitted to clinical medical databases. Electronic databases in the project will employ subject codes that cannot be linked directly to participants without a "key", possessed only by the study investigators in a secure location, and maintained separately from the databases. Databases will be housed on protected UM servers. Personal information that would directly identify study subjects will not be used in any publications or presentations resulting from this research study, unless separate written permission is given by the subject (or proxy). Any superfluous records will be shredded.

Clinical and Behavioral Testing: Care will be taken to minimize distress. The study protocol is designed with the minimum number of procedures and tasks, so as to minimize participant burden. Subjects will be addressed in a courteous manner that does not infringe the patient's dignity. These individuals are prepared to respond to patient anxiety, concern and other behavioral changes as appropriate to the situation. Offering breaks and

reassuring subjects will further minimize risks when necessary. All study visits will occur in the morning. Subjects studied in the overnight “off state” will take their medication as soon as study procedures are concluded.

E. Safety Monitoring:

Review of study procedures and adverse effects will be performed on a monthly basis. The PI will be responsible for monitoring any break in confidentiality and for reporting any adverse events following University of Michigan IRB guidelines. For purposes of this study, an AE is defined as any unfavorable or unintended change in structure, function, signs, or symptoms temporally associated with participation in this study, whether or not a causal relationship with the study has been established. Clinically significant abnormalities may be considered an AE if deemed appropriate by the PI. Unexpected worsening of a pre-existing condition is also considered an AE, as is the discovery of an abnormal finding during physical exam that was not included in the medical history. Breaches of confidentiality will be considered related to the research whenever they occur and will be reported. Withdrawals from the study and the reason for these withdrawals will also be reported.

The PI and Co-I are in daily contact with the project research staff testing the participants, scoring and entering data, and will monitor their procedures to ensure that confidentiality is maintained. The PI will ensure that the IRB is notified of any adverse event following the IRB guidelines. Expected and unexpected serious (including fatal) adverse reactions and major unresolved disputes between the research investigator(s) and the research participant or between research investigator(s) will be expeditiously reported to the IRB of the University of Michigan. At the time of renewal, the IRB will be provided with a summary indicating the frequency of the monitoring, cumulative adverse event data, information regarding participant safety or ethics changes, confidentiality issues, benefit-to-risk changes and recommendations on continuing, changing or terminating the study.

For independent oversight, [name], a Movement Disorder neurologist with considerable trial experience, will act as a DSMB. [name] will meet with the study team to review the protocol prior to study initiation, 6 months after study initiation, and then yearly. [name] will receive a study charter that empowers him to recommend significant study changes, including study termination. All AEs will be immediately communicated to [name] for review.

Definitions:

An Adverse Event is any undesirable experience occurring in a subject during a clinical trial, whether or not considered related to the investigational protocol. For reporting purposes, we will distinguish among pre-existing conditions and trial-emergent adverse events.

Pre-Existing Conditions (i.e., undesirable experiences, signs, or symptoms that begin prior to Study Procedures) will not be reported as adverse events unless they worsen in intensity or frequency after study entry (i.e., satisfy definition of Trial-Emergent, below).

Trial-Emergent Adverse Events are undesirable experiences, signs or symptoms that begin or worsen in intensity or frequency after the Screening Visit, and prior to administration of study drug at the Imaging Visit. These will be reported as adverse events.

Serious Adverse Event: A serious adverse event is an adverse event that is fatal or life-threatening, or results in hospitalization, prolongation of hospitalization, persistent or significant disability/incapacity, or a congenital anomaly/birth defect. A life-threatening adverse event is an adverse event that, in the view of the investigators, places the subject at immediate risk of death from the reaction, as it occurred.

Unexpected Adverse Event: An unexpected adverse event is an experience not previously reported or an adverse event that occurs with specificity, severity or frequency that is not consistent with the investigator's prior experience with the research methods.

Relationship to Research Protocol: The assessment of the relationship of an adverse event to the study protocol (none, remote, possible, and probable) is a clinical decision based on all available information at the time of resolution or stabilization. The following definitions of the relationship between the study procedures and the adverse event (including serious adverse events) will be considered:

Remote (unlikely, doubtful, improbable): The time course of the study procedure(s) and the occurrence or worsening of the adverse event makes a causal relationship unlikely and another cause is probable.

Possible: The time course of the study procedure(s) and the occurrence or worsening of the adverse event is consistent with a causal relationship, but another cause cannot be ruled out. OR The time course of the study procedure(s) and the occurrence or worsening of the adverse event is not consistent with a causal relationship but no alternative cause can be identified. If the Investigators are unable to assess causality, the adverse event will be considered “Possible” by definition and not “Remote.”

Probable: The time course of the study procedure(s) and the occurrence or worsening of the adverse event is consistent with a causal relationship, and no other cause can be identified.

Intensity/Severity of an Adverse Event: In addition to assessing the relationship of the administration of the investigational product/procedure to adverse events, an assessment is required of the intensity (severity) of the event. The following classifications will be used:

Mild: A mild adverse event is usually transient in nature and generally does not interfere with normal activities.

Moderate: A moderate adverse event is sufficiently discomforting to interfere with normal activities.

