b) Subjects will be studied at pre-treatment baseline and 2-3 months after L-dopa treatment initiation and regimen stabilization. We will only enroll drug-naïve subjects about to start treatment with L-dopa. Subjects will be studied in OFF and ON acute treatment states at baseline and after LDR induction. There will be 4 measurement states: at baseline prior to chronic treatment initiation (OFF-No LDR); at baseline after a standard, acute oral dose (25/250 carbidopa/L-dopa) of L-dopa (ON-No LDR), 2 months after initiation of chronic, stable L-dopa treatment but with no L-dopa for 10-12 hours prior to evaluation (Practical OFF-LDR), and after subjects’ usual L-dopa dose (ON-LDR) (**Table 1**).

Table 1:

OFF-No LDR	Baseline - Treatment Naïve Subject
ON-No LDR	Baseline - Treatment Naïve Subject After Acute L-Dopa
OFF-LDR	Chronically Treated – “Practical Off” State
ON-LDR	Chronically Treated – After Usual L-Dopa

Practical ON and OFF state measurements will be counterbalanced across individuals. We will recruit both male and female PD subjects, though we expect more male subjects as PD is more common in men. This is a within subjects design and randomization per se is not used. Blinding of study conditions is not feasible. It would be potentially interesting to include a placebo LDR induction arm, but denying PD subjects effective treatment is not ethical. Data analysis will be blinded. It would also be interesting to include a normal subject arm, but this is ethically problematic as it would involve chronic L-dopa treatment. If, however, we obtain results confirming our hypotheses, we will explore inclusion of normal controls in the next phase of experiments.

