e) Analysis Plan: Hypothesis 1A: Our primary comparisons will be performance on the incentive motivation tasks before and after LDR induction. We predict that improved performance on the incentive motivation tasks will be apparent between the OFF-No LDR and Practical OFF-LDR conditions but not in comparisons between the other conditions. Data will be analyzed via 2-Way Repeated Measures ANOVA followed by post-hoc tests with incentive level and treatment condition as the factors and multiple comparison adjustments. Based on the Schmidt et al. data³⁶, we estimate that achieving power of 0.9 at an effect size of $r^2 = 0.15$ requires complete data from 16 subjects. Based on experience with complex, serial imaging studies, we project a 10% dropout rate (~2 subjects). To compensate for dropouts, we will recruit 20 subjects. Hypothesis 1B: We will correlate changes in performance on the incentive motivation task with the change in tapping rates with Pearson or Spearman correlation tests. Hypothesis 1C: We will correlate the results of the amplitude modulation based and grip strength based incentive motivation tasks with Pearson or Spearman correlation tests.

Interpretations and Potential Problems: If our predictions are correct, we will validate the connection between the LDR and partial restoration of vigor modulation. Falsifying this hypothesis will be equally valuable as it would direct research on the LDR towards different features of striatal DA action. We may, for example, find a relationship between the SDR and improved vigor modulation, which would direct research towards the mechanisms of the SDR. As discussed above, prior experiments evaluating vigor modulation in PD have not taken the LDR into account. We may find no clear relationship between vigor modulation and bradykinesia. This would be important as it would cast doubt on the widely accepted concept that PD bradykinesia is the consequence of altered vigor modulation, and potentially re-direct research in this field.

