Subject recruitment is a potential obstacle to study completion. Our clinics follow ~1300 PD subjects with ~200 new PD patient visits per year. Our group successfully recruited for trials requiring untreated PD patients such as STEADY-PD and SURE-PD. Our group expanded this past summer with the addition of 2 faculty Movement Disorder specialists primarily committed to clinical practice. Treatment with dopamine agonists is an exclusion criterion and will not affect recruitment. Our Movement Disorders group is conservative in terms of treatment recommendations and the overwhelming majority of our patients initiate therapy with L-dopa monotherapy. If recruitment lags, we will recruit through the Michigan Parkinson Foundation, the major lay PD organization in Michigan with 71 affiliated support groups and a mailing-email list of ~15,000 (see attached LOS). These experiments are straightforward, using simple behavioral tasks. A potential problem is that some patients experience nausea with initial L-dopa treatment, which could

complicate the ON-No LDR assessment. We will reduce the possibility of nausea by 48 hour pretreatment with the peripheral decarboxylase inhibitor carbidopa. Another potential problem is enrollment of subjects with one of the PD mimics (Multiple System Atrophy, etc.). An advantage of our design is that we will be evaluating subjects after treatment initiation, allowing us to gauge treatment responses. Subjects not improving with L-dopa treatment, defined by the MDS criteria of $\geq 30\%$ improvement in MDS-UPDRS_{III} score, will be excluded.

Specific Aim 2: To use a saccadic eye movement task to assess saccadic eye movement vigor in response to stable value signals in recently treated PD subjects before and after LDR induction.

Hypothesis 2: LDR induction will result in partial restoration of saccadic eye movement vigor in response to previously learned stable value signals in PD subjects in the “practical off” state.

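### The four-state repeated-measures ANOVA has no provision for a missed state, so a subject who lacks only ON-No LDR would conventionally lose both OFF measurements that form the predicted contrast

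*Combined protocol and SAP*

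**What the plan says.** All of this is in the combined protocol and SAP, mostly in section C, Specific Aim 1.

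- **States.** Procedures b) and Table 1 define four: OFF-No LDR, ON-No LDR, Practical OFF-LDR and ON-LDR.
- **Method.** The Analysis Plan (item e) prescribes "2-Way Repeated Measures ANOVA followed by post-hoc tests", the two factors being the incentive level and the treatment condition. It also calls for "multiple comparison adjustments", without naming a procedure.
- **Predicted contrast.** Improvement "will be apparent between the OFF-No LDR and Practical OFF-LDR conditions but not in comparisons between the other conditions". Under Specific Aim 2, the same pair of OFF states is named as the primary comparison.
- **Sample size.** At an effect size of r² = 0.15, "we estimate that achieving power of 0.9" "requires complete data from 16 subjects". Dropout of 10% (about two subjects) is projected from imaging studies, and 20 are to be recruited.
- **Risk to one state.** Interpretations and Potential Problems notes that "some patients experience nausea with initial L-dopa treatment", that this could complicate the ON-No LDR assessment, and that 48 hours of carbidopa pretreatment will lower the chance of it. No rate is given.
- **Missing data.** There is no rule for a missed state, no imputation and no mixed model. Nor does the plan say that subjects with incomplete data will be dropped.

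**The concern.** A conventional repeated-measures ANOVA needs every cell of the design for each subject. With treatment condition at four levels, a subject with three good states drops out of the omnibus test. The state that the plan itself flags as vulnerable, ON-No LDR, is not part of the predicted contrast. It serves the short-duration-response comparison in Procedures c) and the prediction of no change elsewhere. A subject who cannot complete that session still has the two OFF measurements on which Hypothesis 1A turns, and the planned method would set them aside.

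The dropout allowance rests on subjects leaving imaging studies, not on the loss of one session, so it does not cover this. Precision in a study of 20 is at stake. If intolerance of the acute dose were related to dopaminergic response, the complete-case estimate could also be biased, but nothing in the documents establishes that link. Specific Aim 2 plans a similar analysis over the same four states and so has the same gap.

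**Working it through.** **Inputs from the plan:** 16 complete subjects, power 0.9, r² = 0.15, 10% dropout, 20 recruited, four states. **Assumed:** two-sided alpha 0.05 (none is stated); an extra ON-No LDR loss rate q, independent of dropout (none is stated).

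**1. The plan's 16.** f² = 0.15/0.85 = 0.176, so f = 0.42. For a within-subject factor with m levels and correlation ρ, the noncentrality is λ = f²·n·m/(1 − ρ).
- m = 4, ρ = 0.3: λ at n = 16 is 0.176 × 16 × 4/0.7 = 16.1; power 0.913; required n = 16.
- m = 2, ρ = 0.5: λ at n = 16 is 0.176 × 16 × 2/0.5 = 11.3; power 0.881; required n = 17.
- Other choices miss: m = 4 needs 22 at ρ = 0 and 12 at ρ = 0.5.

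So 16 is reachable, but only under inputs that the plan does not state. Below, power of 0.9 at n = 16 is taken at face value.

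**2. The dropout allowance.** 16/0.9 = 17.8, so 18 recruits would cover 10% dropout. Recruiting 20 leaves 20 × 0.9 = 18 expected, two above the target.

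**3. Extra loss of ON-No LDR under complete-case analysis.** The number complete is K ~ Binomial(20, 0.9(1 − q)), with expectation 18(1 − q). For power, a two-sided paired t test with 0.9 at n = 16 implies a standardised mean difference dz = 0.868. By the noncentral t, power is then 0.78 at n = 12, 0.85 at 14, 0.90 at 16 and 0.93 at 18. Average power is the sum over k of P(K = k) × power(k).

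| q (assumed) | Expected complete | P(at least 16) | Average power |
|---|---|---|---|
| 0 | 18.0 | 0.957 | 0.93 |
| 5% | 17.1 | 0.847 | 0.92 |
| 10% | 16.2 | 0.673 | 0.90 |
| 15% | 15.3 | 0.477 | 0.88 |
| 20% | 14.4 | 0.302 | 0.85 |

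The expected number falls below 16 only when q exceeds 1 − 16/18 = 11%.

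**4. The same loss with the OFF data kept.** Subjects who lack only ON-No LDR still contribute to the contrast, so the first row applies at every q: 18 expected, 0.957, and power about 0.93.

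**5. A loss that the fix does not touch.** Subjects without at least 30% improvement in MDS-UPDRS III are excluded after enrolment, outside the 10%. If that removed 10% (assumed), the expectation would be 20 × 0.9 × 0.9 = 16.2 and P(at least 16) = 0.673. With q = 10% as well, these become 14.6 and 0.334.

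**The case against.** The plan contains no exclusion rule. Dropping incomplete subjects is how the omnibus test conventionally behaves, not something the plan states. A post-hoc test of the two OFF states could use everyone who has both, and the plan does not forbid it. This stands: the weakness is a named method combined with silence, not a declared exclusion.

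A reader might infer that the 16 complete subjects are easily lost. The documents do not support that. They give no nausea rate, they plan a mitigation, a complicated session is not necessarily a missing one, and 20 recruits exceed the 18 that the dropout rate requires. Every shortfall in the table comes from an assumed rate.

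A reader might also apply an independent 10% loss to each state: 18 × 0.9⁴ = 11.8 with all four. But the states come in pairs at two time points, so losses would probably cluster, and missing the whole second assessment is largely the dropout already counted. In that scenario subjects with both OFF states number 18 × 0.9² = 14.6, also below 16. Much of that shortfall is therefore neither caused by the ANOVA nor cured by replacing it.

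The ON states also matter to Hypothesis 1A, because the plan predicts no improvement in the other comparisons. That is a reason to keep all four states in the model, not to require all four from every subject. Finally, a prespecified paired OFF contrast with a missing-state rule would be simpler and would protect the primary comparison. It is an acceptable minimum, but it leaves the other comparisons without a common model.

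**Conclusion.** The concern holds in a limited form. The method named, in its conventional form, ties the OFF-to-OFF contrast to a state that the contrast does not use and that the plan recognises as vulnerable; neither a missing-state rule nor the dropout allowance covers this. On the plan's own figures the target is met with probability 0.96. The cost depends on an ON-No LDR loss rate that the documents do not give. Up to about 10% the expected number stays above 16 and average power stays near 0.90; at 20% power is about 0.85 and the chance of reaching 16 is 0.30.

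These figures assume losses independent of dropout, a two-sided alpha of 0.05 without multiplicity adjustment, and the stated power taken at face value. Bias from complete-case analysis is a possibility only. The change is worth making because the loss is avoidable and each subject counts in a study of 20, not because the study is shown to be underpowered.

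**What to change.** In the Analysis Plan for Hypothesis 1A, make the primary analysis a linear mixed model fitted to all available states, with incentive level, treatment condition and their interaction as fixed effects, subject random effects, and Kenward-Roger degrees of freedom. Name the OFF-No LDR versus Practical OFF-LDR contrast in the incentive effect as primary. Keep the complete-case ANOVA as a sensitivity analysis.

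For Specific Aim 2, use the analogous model on the VDAOC outcome. That task has no incentive levels, so put distractor type in their place where applicable.

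The cost is wording. The plan must state a covariance structure and accept a missing-at-random assumption, which is weaker than what the complete-case ANOVA needs. The model does not recover dropouts or subjects excluded as non-responders, so the recruitment allowance should be justified separately for those losses.

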It is not feasible to train PD subjects on hundreds of fractal images. We will use an analogous task validated well in humans; value driven attentional oculomotor capture (VDAOC).⁴¹⁻⁴³ A probabilistic learning task is used to train subjects to associate a salient visual stimulus (color) with reward. In a test phase, the previously rewarded stimulus is presented in task-irrelevant context as a distractor. Saccades to the test phase target and distractor are assessed, including percentage of saccades to distractor or target, saccade latency, and saccade duration. Previously rewarded distractor stimuli capture initial saccades and the magnitude of VDAOC is assessed. This task is accompanied by striatal dopamine release.⁴⁴ Subjects are trained in a single session and attentional capture is remarkably durable; it persists in test phase experiments months after a single training session.⁴⁵ To duplicate the approach used by Hikosaka et al., PD subjects will be trained on reward-color association prior to initiation of L-dopa therapy. VDAOC will be measured in 4 measurement states described above (**Table 1**). Saccades will be evaluated with an Eyelink tracker with a sampling rate of 250 Hz. If we again assume a modest effect size of $\eta^2 = 0.15$, 16 subjects will be sufficient to achieve a power of 0.9. To guard against dropouts, we will target enrolling 20 subjects. Data analysis approach will be similar to that proposed for **Specific Aim 1**.

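### The stated 0.9 power with 16 completers is not tied to the adjusted OFF-No LDR versus Practical OFF-LDR contrast, and null results are given weight without a precision criterion

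*Combined protocol and SAP*

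**What the plan says.** **Aim 1 (Section C, Specific Aim 1, item e, Analysis Plan).** For Hypothesis 1A, "Our primary comparisons will be performance on the incentive motivation tasks before and after LDR induction". Improvement is predicted between OFF-No LDR and Practical OFF-LDR, "but not in comparisons between the other conditions". The analysis is a two-way repeated measures ANOVA, then "post-hoc tests with incentive level and treatment condition as the factors and multiple comparison adjustments". The sample size statement follows: "we estimate that achieving power of 0.9 at an effect size of $r^2 = 0.15$ requires complete data from 16 subjects". The dropout allowance is 10%, and 20 subjects are recruited.

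**Aim 2.** Procedures takes the same 0.15, now written as eta-squared, and says "16 subjects will be sufficient to achieve a power of 0.9". The Interpretations paragraph names OFF-No LDR versus Practical OFF-LDR as the one primary comparison and describes the analysis as similar to Aim 1.

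**Null results.** The Aim 1 Interpretations paragraph says "Falsifying this hypothesis will be equally valuable as it would direct research on the LDR towards different features of striatal DA action". On finding no clear relationship between vigor modulation and bradykinesia it says "This would be important as it would cast doubt on the widely accepted concept" that altered vigor underlies bradykinesia. The Aim 2 Interpretations paragraph treats a validated Hypothesis 1 with a falsified Hypothesis 2 as certain evidence against the proposed mechanism. The documents define neither falsification nor a margin, interval rule or smallest effect of interest.

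**The concern.** Two things are at stake.

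The first is which test has 0.9 power. The deciding contrast is one pair out of four states. As item e) is worded, it falls under the multiplicity adjustment and is not exempted. The sample size sentence does not say what effect the 0.15 describes, what alpha or within-subject correlation was used, or whether the adjustment was included. If 0.9 belongs to an unadjusted or omnibus test, the test that settles Hypothesis 1A may have noticeably less.

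The second is what a null result means. Three statements give a null a scientific consequence, and none requires the estimate to be precise enough to bear it. With about 16 subjects, an imprecise null could be reported as having falsified a hypothesis.

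**Working it through.** **Inputs from the documents:** effect size 0.15, 16 completers, power 0.9, four measurement states, two Aim 1 tasks, 20 recruited, 10% dropout.

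**Assumed:** two-sided alpha 0.05; within-subject correlation ρ of 0.3, 0.5 or 0.7; sphericity; Bonferroni over 3 comparisons (the one LDR and two SDR comparisons in Aim 1 item c) up to 6 (all pairs of four states). The documents give none of these.

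**1. The plan's own figure.** f² = 0.15/0.85 = 0.176, so f = 0.420. For a within-subject factor with m levels, λ = f²·n·m/(1−ρ), with (m−1) and (n−1)(m−1) degrees of freedom.
- Four states, ρ = 0.3: λ = 0.1765×16×4/0.7 = 16.13; 3 and 45 df; power 0.91.
- Two states, ρ = 0.5: λ = 0.1765×16×2/0.5 = 11.29; 1 and 15 df; power 0.88 (0.90 needs ρ = 0.53).

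The stated figure is therefore reproduced approximately for an unadjusted test. Other readings do not return it: four states at ρ = 0 give 0.78. The inputs allow 0.9 but do not determine it.

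**2. The deciding contrast.** Paired t-test, 15 df, d_z = 2f/√(2(1−ρ)), noncentrality d_z·√16.

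| ρ | d_z | Unadjusted | Bonferroni 3 | Bonferroni 6 |
|---|---|---|---|---|
| 0.3 | 0.71 | 0.76 | 0.57 | 0.45 |
| 0.5 | 0.84 | 0.88 | 0.74 | 0.63 |
| 0.7 | 1.08 | 0.98 | 0.94 | 0.88 |

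At ρ = 0.5 the adjustment costs 0.14 to 0.25 of power.

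**3. What 16 completers can detect.** For one task at two-sided 0.05, power is 90% at d_z = 0.87 and 80% at d_z = 0.75. This form needs no assumed correlation. For Aim 1's two tasks, each with d_z = 0.87, power is about 0.83 per task with Bonferroni over two. If both must succeed and are independent, it is about 0.90×0.90 = 0.81.

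**4. Precision of a null.** For the contrast, the 95% half-width is t(0.975; 15)/√16 = 2.131/4 = 0.53 SD of the paired difference. For an observed r = 0 it is tanh(1.96/√13) = 0.50. Neither excludes a moderate effect such as d_z = 0.5 or r = 0.4. No power is stated for Hypothesis 1B; 90% needs |r| of about 0.7.

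**5. Miss rates, only if non-significance is read as falsification.** At an assumed true d_z of 0.5 the contrast is non-significant in 54% of trials unadjusted, and in 72% to 81% with Bonferroni over 3 to 6.

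**The case against.** **Sample size.** A reader might infer that 16 is too few or that the calculation is wrong. The documents do not support that. Common assumptions return about 0.9. The estimate rests on a cited dataset that is not reproduced, so its variance and correlation are unknown. At a correlation of 0.7 the adjusted contrast still has 0.88 to 0.94. What stands is narrower: the 0.9 is not linked to the adjusted contrast.

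**Adjustment.** Item e) names primary comparisons before it mentions post-hoc tests, and Aim 2 names one primary comparison. The adjustment may be meant only for the rest. That is a fair reading, but the text does not state it. If it is the intention, the change costs nothing.

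**Predicted pattern.** A reader might infer that predicting no improvement in the other comparisons is self-contradictory, because ON-LDR cannot match two states that differ. That takes the phrase to cover all five other pairs. Item c) points instead to the two ON versus OFF comparisons, and the prediction is then coherent. In simulation with both LDR states raised equally by 2f, correlation 0.3 and 16 subjects, that three-comparison pattern appears in about 70% of trials unadjusted and 44% at 0.05/6. What remains is that the comparisons are not listed, and that non-significance would not show an absence of change.

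**Null wording.** The sentences are prospective discussion, not decision rules, and Aim 2 offers impaired value encoding as another explanation for a null. The documents never equate falsification with p > 0.05, so the miss rates are conditional. But the alternative explanation is biological. It does not address imprecision, and no other passage does.

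**Conclusion.** This is a worthwhile, low-cost improvement, not an error of arithmetic. The power half holds only as not shown. For the adjusted contrast, the range from 0.45 to 0.94 reflects assumed correlations and an assumed 3 to 6 comparisons, not figures in the plan. The null-result half is firmer: the half-widths of 0.53 SD and 0.50 need only n = 16 and standard 95% intervals. With that precision, a contrast or correlation observed near zero would not justify the weight the Interpretations paragraphs give it.

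**What to change.** Keep 20 subjects.

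1. **Aim 1, item e).** Make OFF-No LDR versus Practical OFF-LDR the single pre-specified primary contrast for each task. Name the ANOVA term it tests (state mean or incentive-by-state change). Test it at two-sided 0.05 without adjustment for the other state comparisons, and adjust only those.
2. **Aim 1, item e), and Aim 2, Procedures.** State power for that contrast on that term: 16 completers give 90% for d_z of about 0.87 and 80% for about 0.75, for one task at 0.05. For Aim 1, say whether either task or both must succeed, and give power for that rule.
3. **Both Interpretations paragraphs.** Treat a non-significant result for Hypothesis 1A, 1B or 2 as inconclusive unless its 95% interval excludes a value stated in advance. Apply the same rule to the comparisons predicted to show no change, and list them.

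**Cost.** Text only; no added subjects or visits. The stated power becomes less favourable, the investigators must choose a value in advance, and many nulls will be reported as inconclusive. With no true effect and 16 subjects, the upper 95% limit falls below 0.5 SD in about 45% to 47% of trials, below 0.75 SD in 80% and below 0.87 SD in 90%.

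More than 16 completers should not be assumed. After 10% dropout 20×0.9 = 18 remain, and the Aim 1 Interpretations section also excludes after enrolment "Subjects not improving with L-dopa treatment, defined by the MDS criteria of" at least 30% on the MDS-UPDRS motor score. The d_z detectable at 90%/80% power is 0.94/0.81 with 14 completers and 0.81/0.70 with 18.
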